20.3.1 Sample Size Rationale

The results of two prospective studies were used to inform the sample size estimation. The Endobronchial Valve for Emphysema Palliation Trial ("VENT Pivotal Trial", IDE#G020230, NCT00129584) was a multi-center, prospective, randomized, controlled study conducted at sites in both the United States and Europe to assess the safety and effectiveness of using the Zephyr EBV device for palliating symptoms associated with severe heterogeneous emphysema. Four hundred ninety two (492) participants were enrolled into the study and randomized to Zephyr EBV Treatment or medical management (control) [16,17]. The Chartis Pulmonary Assessment System study is a recently completed prospective post-market study that was conducted in Germany, The Netherlands, and Sweden. The primary objective of the study was to quantify the accuracy of the Chartis System when used to identify targeted treatment lobes as having or not having inter-lobar CV in patients with emphysema who were to be treated using endobronchial valves (26). The results of both the VENT Study and the Chartis System study showed that treatment effect with the endobronchial valve is correlated with lack of inter-lobar CV [16,17,25].

Patients in the VENT Study and in the Chartis Study who were considered to have little or no inter-lobar CV contributed the information used for the sample size estimate. Patients who have little or no lobar CV in the targeted treatment lobe are expected to be good responders to endobronchial valve treatment. For the sample

size estimate, a 'responder' was considered to be a study participant who had $\geq 15\%$ improved FEV₁ after EBV treatment.

Based on the results of these studies, the responder rate in the EBV Study Treatment Group is expected to be approximately 35% at 1 year. The responder rate for the control group is not expected to exceed 10% at 1 year. Assuming a two-sided 0.05 alpha level, study power of 90%, and 2:1 allocation random assignment, a sample size of 147 will be adequate to test for superiority.

The study sample size will be increased to 183 in order to allow for 20% lost to follow-up and incomplete data. Each study site will be allowed to enroll a maximum of 25 study participants.

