The study hypothesis will be tested again at the end of the study. The Z-statistic will be calculated again, and by taking into account the interim analysis, will have a final critical boundary value of 2.004, per the nTerim program. If the trial is not stopped as a result of the interim analysis, then the final Z-statistic must be greater than or equal to 2.004 in order to reject the null hypothesis at the final analysis (at the overall 2-sided 5% significance level). Test statistic is "Z" as defined as:

$$Z = \frac{p_T - p_C}{\sqrt{p(1 - p)\left(\frac{1}{n_T} + \frac{1}{n_C}\right)}}$$

Where,

 p_T and p_C are the proportions of success for the primary endpoint in the treatment and control groups, respectively, *p* is the pooled estimate of the success rate, and

 n_T and n_C are the sample sizes obtained in the treatment and control groups,

respectively. Two sets of (p, p_T , p_C , n_T , n_C) will be obtained: one at the interim analysis and one at end of the study.

B. Analysis of the Secondary Effectiveness Endpoints

The following describes the analysis techniques to be used for each of the secondary endpoints. To control the family-wise type I error rate at 5%, the Hochberg step-up procedure will be utilized (Hochberg, 1988).

a. FEV₁

Difference between study arms in 'absolute change from baseline' for FEV1 score at 1 year. Descriptive statistics will include means, standard deviations and 95% confidence intervals. An analysis of covariance (ANCOVA) with factor of treatment and baseline FEV1 as a covariate will be used to test the difference between treatment arms. P-value will be adjusted for multiple imputation.

b. 6-Minute Walk Distance (6MWD)

Difference between study arms in 'absolute change from baseline' for 6MWD at 1 year. Descriptive statistics will include means, standard deviations and 95% confidence intervals. An analysis of covariance (ANCOVA) with factor of treatment and baseline 6MWD as a covariate will be used to test the difference between treatment arms. P-value will be adjusted for multiple imputation.

c. St. George's Respiratory Questionnaire (SGRQ)

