- For study participants with truncated data (e.g. participants who drop out or are lost to follow-up), a multiple imputation strategy will be performed using the propensity score method. In brief, for a particular outcome, the propensities for study participants to have missing data (for each treatment group separately), modeled by logistic regression, are grouped into strata based on percentiles of the logistic propensity score model. Within a stratum, a study participant with a missing observation has an imputed value assigned by randomly choosing a value from among the study participants in the same stratum with non-missing observations. This procedure will be repeated 20 times on the entire dataset, resulting in 20 different 'complete' datasets allowing for estimation of the effect on the outcome of interest, accounting for missing data.

An additional analysis for the primary endpoint will be performed based on not imputing data. All partial data that is available on subjects who drop out during the course of the study will be included. In addition, sensitivity analyses such as worse-case or best-case imputation will be performed although it is recognized that they are biased.

Missing data for secondary endpoints will be imputed using the same methodology described above. Subject death prior to the 1-year visit date will be imputed baseline carried forward (0-point change).

- X. Comparison of Crossed-Over Control versus Study Treatment Outcomes
 - a. Effectiveness Outcomes

omparison based on paired Control versus EBV Treatment differences)				
Variable	Unit	Values Statistically Evaluated		
Forced Expiratory Volume (FEV ₁)	>15% improved	percentage of participants		
FEV ₁	Liters	mean absolute change		
FEV ₁	percent	mean percent change		
SGRQ Total Score	Points	mean absolute change		
mMRC Score	semi-quantitative	mean absolute change		
	scale score			
6-Minute Walk Distance	Meters	mean absolute change		
6MWD – subjects stratified by	meters	mean absolute change		
distance walked at baseline				
6MWD	25 meters	percentage of participants		
	improved			
DLco	percentage	mean absolute and percent change		
Residual Volume (RV)	liters	mean absolute and percent change		
Inspiratory Capacity (IC)	liters	mean absolute and percent change		
Total Lung Capacity (TLC)	liters	mean absolute and percent change		
RV/TLC	ratio	mean absolute change		
IC/TLC	ratio	mean absolute change		

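### The hot-deck in SAP section IX, followed literally, leaves out donor uncertainty, so the primary comparison's standard error is modestly too small (about 2 to 5% at 20% missing)

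*SAP*

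**What the plan says.** SAP section IX (Patient Accountability and Missing Data) makes the imputed analysis the primary one and treats missing FEV₁ in three ways. Death before the 1-year visit counts as failure. Intermittent gaps are filled by linear interpolation. Truncated data, from dropout or loss to follow-up, go to multiple imputation by a propensity score method. For that third group a logistic model for missingness is fitted in each arm, participants are grouped by percentiles of the score, and a participant with a missing value "has an imputed value assigned by randomly choosing a value from among the study participants in the same stratum with non-missing observations". The cycle is repeated 20 times. Superseded Appendix 19 of the protocol describes the same draw.

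The rule reaches further than the primary endpoint: "Missing data for secondary endpoints will be imputed using the same methodology described above", except that deaths there take zero change. On combining the datasets, SAP section IV.B says only, for each secondary endpoint, "P-value will be adjusted for multiple imputation".

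Protocol 20.3.1 gives the planning figures. The sample size was "increased to 183 in order to allow for 20% lost to follow-up and incomplete data".

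**The concern.** A proper multiple imputation must carry two sources of variation: the scatter of individual values around the distribution they come from, and the uncertainty about that distribution, which is itself estimated from a finite set of observed participants. Drawing straight from a fixed donor pool carries only the first. The 20 datasets therefore resemble one another too closely, and the combined variance is too small. More imputations do not cure this, and neither does a correct combination rule.

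The primary test has a boundary set to preserve 5% overall, and the three secondary endpoints are tested by Hochberg at a family-wise 5%. A standard error that is too small would erode both guarantees.

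**Working it through.** **Inputs from the documents.** Protocol 20.3.1 plans on 35% responders with EBV and at most 10% in controls, and states: "Assuming a two-sided 0.05 alpha level, study power of 90%, and 2:1 allocation random assignment, a sample size of 147 will be adequate". Also N = 183 with a 20% allowance; 190 actually enrolled (SAP, Study Design); 20 imputations (SAP IX); final boundary 2.00360 (SAP IV.A, Table 2).

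**Assumed, not in the documents.** Five strata per arm; Rubin's rules; missingness unrelated to outcome; the imputed quantity is the responder status or the change score.

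**Reproducing the plan's figures.** For 10% v 35%, 2:1, two-sided 0.05 and 90% power, the pooled-variance formula with continuity correction gives 49 + 98 = 147, as stated (132 without the correction). 147/0.8 = 183.75, so 184 against the stated 183; 1 − 147/183 = 19.7%. Spending: 0.05 × 0.5^2.3 = 0.01015, and bounds 2.57057 and 2.00360 give overall alpha 0.0500. The final look alone has nominal level 0.0451, which is the yardstick for the final-look error rates below.

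**Formula.** Let f be the fraction imputed and M = 20. In units of σ²/n for one arm:

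- Direct draws: reported variance T = 1 + (1 + 1/M)f; true variance V = 1/(1−f) + f/M.
- Donors resampled first: T = V = 1 + (1 + 1/M)·f/(1−f).

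At f = 0.20 with direct draws: T = 1 + 1.05 × 0.20 = 1.21; V = 1.25 + 0.01 = 1.26; T/V = 0.960; SE ratio √0.960 = 0.980. With resampling: T = 1 + 1.05 × 0.25 = 1.2625 = V.

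| f | SE ratio, direct draws | Nominal level at 2.0036 becomes |
|---|---|---|
| 0.05 | 0.999 | 0.0454 |
| 0.10 | 0.995 | 0.0462 |
| 0.15 | 0.989 | 0.0476 |
| 0.20 | 0.980 | 0.0496 |

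**Simulation of the primary test.** 122 v 61, pooled Z against 2.0036, no true difference, 40,000 trials per cell (Monte Carlo SE about 0.1 point). Entries are for null responder rates of 10/20/30%.

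| Missing | Draw | Reported/true SE | Final-look type I error |
|---|---|---|---|
| 10% | direct | 0.982/0.985/0.983 | 4.8/4.9/5.1% |
| 10% | resampled | 0.986/0.989/0.992 | 4.7/4.8/4.6% |
| 20% | direct | 0.964/0.957/0.964 | 5.2/5.7/5.4% |
| 20% | resampled | 0.979/0.988/0.986 | 4.9/4.9/4.9% |

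With essentially no missing data the same program gave 4.4 to 4.6%, so it is calibrated. Smaller runs at 20% missing put the direct-draw SE ratio between 0.948 and 0.971. A separate run of 6,000 replicates gave 4.8 to 5.6% direct against 4.9 to 5.0% resampled.

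Resampling does not return the error fully to 4.5%. Strata are small: with five in a control arm of 61, each holds about 12 participants and, at 20% missing, about 10 donors.

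**Secondary endpoints.** In ANCOVA simulations at 20% missing (1,500 trials), direct draws gave SE ratios of about 0.95 to 0.97 when outcome and baseline correlated at 0 to 0.3, and about 0.99 to 1.01 at 0.6. A further check at 10% missing and correlation 0.6 gave 1.03, with type I error 4.2%. Applying the formula ratios to all three endpoints, with assumed correlations of 0.3 to 0.5 between them, gives Hochberg family-wise error of 4.7 to 5.0% at 10% missing and 5.1 to 5.5% at 20%.

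**The case against.** The SAP presents its description as a summary of a named method, and its software section names SAS (or StatXact) without an imputation procedure or option. The summary also omits the number of strata and the combination rule, so silence on one internal step does not prove that step will be left out. This stands. A reader might infer that the trial's standard errors will certainly be too small; the documents support only that the draw, as stated, omits the step. It does not follow that the text is harmless, because the draw is stated explicitly and a statistician coding it as written gets the deficient version.

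A reader might also infer that the shortfall applies equally to every endpoint. It does not: the secondary analyses adjust for baseline, and there it can disappear.

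A third tempting reading comes from simulating an unadjusted comparison of means (127 v 63) at 20 to 21% missing, which gives a type I error of 6.1 to 6.5%. That is not the SAP's primary test, and with donors resampled the same simulation still gives 5.4 to 5.5%. Only about 0.6 to 1.1 points belong to this defect.

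The 20% figure is also close to an upper bound on the planning assumption. It was set "in order to allow for 20% lost to follow-up and incomplete data", whereas deaths and intermittent gaps never enter the hot-deck. Finally, the SAP prespecifies a primary analysis without imputation and worst- and best-case analyses, so a conclusion that hung on this difference would probably show. That limits the harm but does not make the stated draw proper.

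**Conclusion.** The point holds in a modest form. Taken literally, the draw in SAP IX understates the standard error of the primary responder comparison even with correct combination. At 20% missing the shortfall is about 2% by formula and 3 to 5% in simulation, with final-look type I error of about 5 to 5.7% against about 4.9% when donors are resampled. At 10% missing it is 0.5% by formula, and the simulated error rates differ by only 0.1 to 0.5 points, which is negligible in practice.

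These sizes rest on the assumed five strata per arm, Rubin's rules and missingness unrelated to outcome. The achieved missing fraction is not in the documents. Overall error across both looks with missing data was not computed. No general claim is made for the secondary ANCOVAs, and family-wise inflation was not shown beyond about 5.1 to 5.5% at 20% missing. The correction is still worth making: the rule governs the primary analysis and the remedy is specific and cheap.

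**What to change.** Add to SAP section IX: for each stratum and each of the 20 imputations, first draw a sample of the observed donors with replacement, of the same size as the donor set, then draw the imputed values from that sample (approximate Bayesian bootstrap); combine the 20 results by Rubin's rules. If the intended program already does this, state it and name the procedure. Give the number of strata at the same time, since it determines how many donors each stratum holds.

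The cost is one or two sentences and slightly wider confidence intervals. A shortfall of about 1 to 2% in the standard error remains when strata are small.

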Adverse events will be categorized into clinically relevant groups (*e.g.:* stable pneumothorax with no intervention, pneumothorax resolved with chest tube insertion in less than 7 days,

prolonged air leak, etc.). Adverse events occurring in the treatment arm will be further categorized by severity and as device-related, procedure-related, or neither, and by those occurring during procedure hospitalization and those occurring post-discharge.

Rehospitalization rates will be reported by study arm on a Per-Patient (PPt) basis and on a Per-Event (PE) basis. In study participants who receive EBV treatment, adverse events will be evaluated by stratifying participants by use of conscious sedation and general anesthesia during the bronchoscopy procedure as well as evaluating number of valves received and sites EBV were placed.

VIII. Mortality

A Kaplan-Meier survival curve for each study arm will graphically display the time to death from the time of randomization and a log rank test will be used to compare Kaplan-Meier curves between study arms. A Cox proportional hazards model will be used to control for study site along with other significant co-variates as applicable.

IX. Patient Accountability and Missing Data

Every effort will be made to collect all data points in the study. The sponsor plans to minimize the amount of missing data by appropriate management of the prospective clinical trial, proper screening of study subjects, and training of participating investigators, monitors and study coordinators.

- The analysis for the primary endpoint will be performed by imputing missing data. Subject death prior to the 1-year visit date will be imputed as failure.
- For study participant FEV₁ data that is 'intermittent', missing outcomes will be imputed by linear interpolation using the FEV₁ value from the latest non-missing data point before the missed data point and the earliest non-missed data point after the missed data point.

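### Dropouts' 1-year values come from donors matched only on the chance of being missing, and nothing requires the dropout's own earlier results to be used

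*SAP*

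**What the plan says.** For participants who drop out or are lost, SAP IX states that "a multiple imputation strategy will be performed using the propensity score method". The probability of being missing is modelled "for each treatment group separately". The propensities, "modeled by logistic regression, are grouped into strata based on percentiles of the logistic propensity score model", define the donor pools, and the missing value is filled by "randomly choosing a value from among the study participants in the same stratum with non-missing observations". Twenty filled-in datasets are produced in this way.

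The method carries over to FEV1, 6MWD and SGRQ: "Missing data for secondary endpoints will be imputed using the same methodology described above". SAP IV.B then tests each by ANCOVA on its own baseline; for FEV1, "An analysis of covariance (ANCOVA) with factor of treatment and baseline FEV1 as a covariate will be used".

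Several features limit the reach of the method:
- Deaths are outside it. For the primary endpoint, "Subject death prior to the 1-year visit date will be imputed as failure"; for the secondary endpoints a death counts as zero change.
- Intermittent FEV1 gaps are interpolated from the participant's own neighbouring values.
- The primary endpoint also gets an analysis without imputation and worst-case and best-case analyses.

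Three things are not stated: the covariates of the logistic model, the number of strata, and whether the donated quantity is 1-year FEV1 in litres, the change, or responder status. No sensitivity analysis for missing data is named for the secondary endpoints.

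**The concern.** Matching on the chance of being missing is not matching on the likely outcome. Two participants can be equally likely to drop out and still have very different lung function, and the method treats them as interchangeable. Earlier results can enter only through the propensity score, and the SAP does not require them to enter at all.

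Those results are already collected. Protocol Sections 14.9 to 14.11 and Appendix 12 schedule spirometry and 6MWD at 45 days and 6 months, and SGRQ at 3 and 6 months. For intermittent gaps the SAP does use the participant's own values. For dropouts, where bias is more likely, it imposes no such requirement.

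If poor early response makes dropout more likely, donors from a pool blind to that response are too good. The responder rate, which is the primary endpoint, is then overstated. If litres are donated, a stranger's 1-year FEV1 is compared with the participant's own baseline. That creates chance 15% responders and blurs the baseline relation on which the ANCOVA relies.

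**Working it through.** **1. The plan's own figure.** Protocol Section 20.3.1 gives 35% against 10%, two-sided 0.05, 90% power and 2:1 allocation (k = 2). The pooled rate is (2×0.35 + 0.10)/3 = 0.2667.
- Control n = [1.960×√(1.5×0.2667×0.7333) + 1.2816×√(0.35×0.65/2 + 0.10×0.90)]² / 0.25² = (1.0615 + 0.5785)²/0.0625 = 43.03.
- With continuity correction: (43.03/4)×[1 + √(1 + 6/(2×43.03×0.25))]² = 48.85, so 49 control + 98 EBV = **147**, as stated.
- 147/0.80 = 183.75, against the stated 183.

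The documents give no figure for imputation bias, so that has to be simulated.

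**2. Simulation inputs.** From the documents: 190 enrolled at 2:1 (about 127:63), 35% and 10% responders, the 20% allowance for loss, 20 imputations, and the final bound 2.004. Assumed, because the documents are silent: SD of percent change 22; baseline FEV1 mean 0.75 L, SD 0.22 L; 6-month to 1-year correlation 0.5 to 0.85; five strata per arm; dropout log-odds rising by 1.0 per SD of worse 6-month change (1.5 in one run).

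**3. Responder difference (20% missing per arm, correlation 0.7, true difference 25.0 points).**
- Donor method, baseline-only propensity: 39.0% − 11.6% = **27.4**.
- No imputation (complete cases): **27.4**, the same.
- Donor method, interim values in the propensity, change donated: 35.2% against 10.1%, difference **25.2** before rounding.
- Regression imputation on baseline, 45-day and 6-month values: 35.2% − 10.2% = **25.0**.

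The excess can be traced by hand. The bias in an arm is the missing fraction times (donated rate − dropouts' true rate).
- EBV: 0.8×39.0 + 0.2×r = 35 gives r = 19.0%, so bias = 0.2×(39.0 − 19.0) = 4.0.
- Control: 0.8×11.6 + 0.2×r = 10 gives r = 3.6%, so bias = 0.2×(11.6 − 3.6) = 1.6.
- Net: 4.0 − 1.6 = 2.4 = 27.4 − 25.0.

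Across correlations and missingness of 20/20, 20/10 and 10/20% (EBV/control), the baseline-only excess ran from about 0.4 to 4.2 points. It was 0.7 at 5% missing and about 0 under completely random missingness.

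**4. ANCOVA effect on FEV1 (mL) and responder difference (points), 300 replicates.**

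| True rates; missing EBV/control | Complete data | Donor: baseline only, change | Donor: interim, change | Donor: interim, litres | Regression |
|---|---|---|---|---|---|
| 35/10; 20/20% | 148; 24.3 | 148; 26.6 | 148; 24.4 | 148; 24.4 | 148; 24.3 |
| 35/10; 20/10% | 149; 25.2 | 158; 28.6 | 149; 25.4 | 149; 26.8 | 149; 25.3 |
| 10/10; 20/5% | 0; −0.2 | 14; 1.0 | 1; −0.2 | 2; 2.4 | 0; −0.1 |
| 20/20; 20/5%, correlation 0.85, slope 1.5 | −2; −0.5 | 20; 2.6 | 0; −0.5 | 0; 2.5 | −3; −0.4 |

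In the two null rows, two-sided ANCOVA rejection (before Hochberg) was 9.7% and 15.7% with baseline only. It was 4.0% and 6.3% with interim values and change, and 3.7% and 5.3% with complete data. The Monte Carlo standard error is about 1 to 2 points. For the primary Z test at 2.004, baseline-only rejection was 6.3% and 4.7%, against 5.0% and 4.3% with complete data, which is no clear inflation.

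**5. Litres donated, interim values in the propensity (20/20% missing).** The control responder rate rises to about 13% against 10%. The baseline slope moves from −0.007 to −0.178. The mean ANCOVA standard error is 35 mL, against 28 mL when change is donated and an empirical SD of 28 mL. At equal dropout the inflation is similar in both arms and largely cancels in the difference; at unequal dropout it does not.

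**6. Individual information kept.** The correlation of the imputed 1-year value with the participant's own 6-month value was 0.0 (baseline only), 0.43 (interim values in the propensity) and 0.66 (regression), at correlation 0.7 and 20% missing. Under completely random missingness the last two were 0.21 and 0.67.

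**The case against.** The strongest reply is that propensity-score imputation is a recognised method, that SAP IX only summarises it, and that a sensible analyst would put interim values into the model and donate change. That version came within about 0.4 points of the truth in every scenario tested. This stands, and it rules out three stronger readings that a reader might reach.

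- *The SAP discards the 45-day and 6-month results.* It does not say so. It leaves the covariates open.
- *Regression imputation is better in every scenario.* On bias it is not: the well-specified donor version is nearly as good. What that version loses is individual information.
- *Valve removal will drive EBV dropout.* Protocol Section 12.0 keeps participants who have secondary valve procedures on the follow-up schedule counted from initial treatment, so removal is not dropout. The 20% in Section 20.3.1 is an overall allowance and says nothing of imbalance or cause.

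Other protections are real. Modelling is within arm, deaths are handled separately, and Appendix 12 schedules spirometry at early termination. The ANCOVA effect was unbiased at equal dropout. Donation of litres is not stated, although the adjacent rule for intermittent gaps works on FEV1 itself, which makes litres a natural reading.

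The checks in the SAP do not settle the matter. The analysis without imputation gave the same 27.4 points as the baseline-only donor method, so agreement between the two would be false reassurance. Worst-case and best-case analyses bound the error without correcting it. Neither is named for the secondary endpoints.

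**Conclusion.** The point holds in a limited form. The planned method ties a dropout's imputed value to that person's earlier results at best indirectly, and the SAP permits versions that overstate the effect as well as one that is nearly unbiased. Without interim values in the propensity model, and with dropout driven by poor early response, the responder difference is too large by roughly 0.4 to 4 points. The ANCOVA effect is biased when dropout is unequal: 158 against 149 mL at 20/10%, and a false 14 to 20 mL under the null at 20/5%. Donating litres inflates responder rates and weakens the baseline relation even when interim values are in the model.

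These sizes are illustrative. They depend on the assumed SDs, correlations, strata and dropout mechanism, and they vanish under completely random missingness. The simulations do not show a materially raised false-positive rate for the primary test.

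**What to change.** In SAP IX, for truncated data only, replace the propensity-stratum draw with multiple imputation by arm, using regression or predictive mean matching for the 1-year value. Predictive mean matching still borrows a donor, but matches on the predicted outcome instead of the predicted chance of being missing.

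- Include baseline and all earlier post-baseline values of the same measure: 45-day and 6-month for FEV1 and 6MWD; 3-month and 6-month for SGRQ.
- Derive 15% responder status from each participant's own baseline.
- Keep the existing death rules.
- Pool at least 20 imputations by Rubin's rules.
- Keep the propensity-stratum method as a sensitivity analysis, for the secondary endpoints too, with its covariates (including interim values), number of strata and donated scale (change) written down.

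The cost is one SAP paragraph, standard software options and a small modelling assumption about how earlier values predict the 1-year value. No new data are needed.

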Statistical Methods V	Clarify that covariate analyses are to be performed on primary and secondary endpoints only. Removed variables that will not have data available for control subjects.	Clarification.
	Deleted "Follow-up" column as no "Follow-up" variables will be used in covariate analysis.	
Safety Analyses VII	Updated to include Control arm in summary of adverse events and specify Fisher's Exact tests of events occurring in at least 3% of either treatment arm.	In place of presenting confidence intervals, adverse event rates for those events occurring in at least 3% of subjects will be compared using a Fisher's Exact test.
Statistical Methods IX	Included imputation strategy for subject deaths and clarified secondary endpoints would utilize same imputation method as primary endpoint.	Subject death prior to endpoint visit should be considered a failure. Secondary endpoints should account for missing data.
Statistical Methods X	Clarification to statistical tests.	Clarification.
Other	Tables and text formatted.	Ease of reading.

Analysis Summary

Study Title: Lung Function Improvement after Bronchoscopic Lung Volume Reduction with Pulmonx Endobronchial Valves used in Treatment of Emphysema (Clinical Protocol 630-0012).

Patient Population: Male and female patients with severe heterogeneous emphysema meeting the study eligibility criteria.

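### Scoring a death as zero change in FEV1, 6MWD and SGRQ gives deaths almost no influence on the three secondary tests, and no alternative death score is planned for them

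*SAP*

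**What the plan says.** SAP Section IX has two death rules. For the primary responder endpoint: "Subject death prior to the 1-year visit date will be imputed as failure". For the secondary endpoints: "Subject death prior to the 1-year visit date will be imputed baseline carried forward (0-point change".

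The secondary endpoints are absolute change at 1 year in FEV1, 6MWD and total SGRQ score. SAP Section IV.B tests them together: "To control the family-wise type I error rate at 5%, the Hochberg step-up procedure will be utilized". Each is compared by a model of the same form; for walking distance it is "An analysis of covariance (ANCOVA) with factor of treatment and baseline 6MWD as a covariate".

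The worst-case and best-case sensitivity analyses are set out in the Section IX paragraph on the primary endpoint. No other death score is named for the secondary endpoints. The Completed Cases analysis (Section III.C) requires attendance at the 1-year visit, so it leaves deaths out. Mortality has its own Kaplan-Meier, log-rank and Cox analyses (Section VIII).

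**The concern.** For a responder endpoint, no change is a failure. For a continuous change score, no change lies inside the range of survivor outcomes. Any survivor whose FEV1 or walking distance falls, or whose SGRQ rises, is scored below a participant who died.

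Protocol Section 1.2 describes declining lung function as the course to be slowed, so worsening survivors are to be expected. Protocol Section 15.1 expects more adverse events in the EBV arm up to day 45 and lists death among the possible events. It does not predict more EBV deaths, but an imbalance is possible. If one occurred, a secondary claim about function or quality of life could be made in nearly the same terms as if nobody had died.

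**Working it through.** **The plan's own figure.** The only sample-size figure is for the primary endpoint: "Assuming a two-sided 0.05 alpha level, study power of 90%, and 2:1 allocation random assignment, a sample size of 147", where "the responder rate in the EBV Study Treatment Group is expected to be approximately 35% at 1 year" and the control rate is at most 10%. It reproduces:

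- Pooled rate = (0.10 + 2 × 0.35)/3 = 0.2667.
- Uncorrected control n = [1.960·√(1.5 × 0.2667 × 0.7333) + 1.282·√(0.10 × 0.90 + 0.35 × 0.65/2)]² / 0.25² = 43.0.
- With continuity correction, n = (43.0/4)·[1 + √(1 + 6/(43.0 × 2 × 0.25))]² = 48.9, so 49 control and 98 EBV, total 147.

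There is no SD, effect size or death rate for the secondary endpoints, so the rest uses assumptions.

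**Inputs.** 190 enrolled (SAP, Study Design). Arms of 127 and 63 are assumed from 2:1. For 6MWD, SD 75 m and a survivor difference of 25 m are assumed, as are the death counts.

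**Where zero falls among survivors.** The share of survivors scored worse than a death is Φ(−mean/SD). It is 37% if the survivor mean is +25 m, 50% if it is 0, and 63% if it is −25 m.

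**Weight of one death.** With d deaths among n, survivor mean m and death score s, arm mean = (1 − d/n)·m + (d/n)·s.

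- At s = 0, one EBV death costs m/127: 25/127 = 0.20 m.
- For contrast, scoring the death as a walk of 0 m from a 300 m baseline costs (300 + 25)/127 = 2.6 m.
- SGRQ, mean gain 8 points, five EBV deaths at zero change: 8 × 5/127 = 0.31 points.
- FEV1, mean gain 0.10 L, eight EBV deaths at zero change: 0.10 × 8/127 = 0.006 L.

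**Direction of the shift under the zero-change rule (6MWD).**

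| Survivor means, EBV / control | Deaths | Difference between arms | Difference without deaths |
|---|---|---|---|
| +25 / 0 | 5 v 1 | 25 × 122/127 = 24.0 m | 25 m |
| +25 / 0 | 8 v 1 | 25 × 119/127 = 23.4 m | 25 m |
| 0 / −25 | any v 1 | 25 × 62/63 = 24.6 m | 25 m |
| −25 / −25 | 8 v 1 | −25 × 119/127 + 25 × 62/63 = +1.2 m | 0 m |

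**Power.** These are simulated for one endpoint at two-sided 0.05, with survivor means of +25 / 0 or 0 / −25. A repeat with baseline-adjusted ANCOVA, and rank ANCOVA for deaths ranked last, agreed within about 2 percentage points.

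| Deaths | Excluded | Zero change | Ranked last | Worst observed value |
|---|---|---|---|---|
| 5 v 1 | 56–57% | 55–58% | about 40% | 31–32% |
| 8 v 1 | 55–56% | 54–57% | about 26% | about 15% |
| 6 v 3 (proportionate) | – | 56% | 48% | 42% |

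With both arms at −25 m and 8 v 1 deaths, the chance of a false result in favour of EBV is about 3%, against a nominal 2.5%.

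**Would the separate mortality comparison show such an imbalance?** As a rough guide on counts, Fisher's exact test gives p = 0.67 for 5/127 v 1/63 and p = 0.28 for 8/127 v 1/63.

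**The case against.** A reader might infer that the SAP contradicts itself, because the Change History row for Section IX says "Subject death prior to endpoint visit should be considered a failure" and that the revision "clarified secondary endpoints would utilize same imputation method as primary endpoint". This does not carry the point. The row is a change log that covers two changes with two reasons. Failure is defined only for the binary endpoint, and zero change can be read as no benefit on a continuous scale.

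A reader might also infer that the rule tilts the secondary tests towards EBV. The working does not support that. If EBV survivors improve, each EBV death at zero lowers the EBV mean. If controls decline, a control death at zero helps the control arm, with about twice the weight (1/63 against 1/127). A shift towards EBV needs decline in the EBV survivors and more EBV deaths, and is then about 1 m.

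It is also fair that deaths count elsewhere: as failures in the primary endpoint, which alone defines study success, and in the mortality analysis. How to score death in a continuous endpoint is a choice of estimand, and harsher scoring costs power even when deaths are proportionate. These points stand, and they argue against replacing the main rule.

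They do not close the gap. A mortality comparison can miss an imbalance that matters to the secondary results. The Completed Cases analysis omits deaths, so it offers no contrast with a rule that acts almost the same way. The cross-reference in Section IX to the same methodology might be read as extending the worst-case analysis to the secondary endpoints, but the SAP does not say so.

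**Conclusion.** The point holds in a limited form. Under the zero-change rule a death outscores every survivor who worsens, and unequal deaths have almost no influence on the three Hochberg-controlled tests. In the 5 v 1 and 8 v 1 cases, power stays within a few points of excluding the deaths, whereas ranking deaths last lowers it to about 40% and 26%. Those gaps show how much the conclusion depends on the death score; they do not measure an error in the zero-change analysis.

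The documents do not show that the rule inflates the EBV effect, and they do not report or predict excess EBV deaths. All effect sizes, SDs, arm sizes and death counts used here are assumptions. The primary endpoint and the mortality analysis are not affected.

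**What to change.** In SAP Section IX, keep the zero-change ANCOVA and add, for FEV1, 6MWD and SGRQ in both arms:

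- An analysis that places all deaths, tied, below the worst survivor (for SGRQ, above the highest increase) and compares arms by rank ANCOVA adjusted for the baseline value. Ranks are formed within each imputed dataset.
- Reporting of this result beside the zero-change ANCOVA, with survivor means and the number of deaths per arm.
- A statement that a secondary claim is described as robust only if both analyses agree, meaning that the Hochberg procedure applied to each set of three p-values gives the same decision.

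Single worst-observed-value imputation should not be used. It rests on one extreme observation and inflates the variance; with 6 v 3 deaths it lowers power to 42%, against 48% for ranking.

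The cost is SAP wording and a small amount of programming, with no new data. The rank result has no natural units, so estimates in litres, metres and points still come from the ANCOVA. The added analysis will look less favourable if EBV deaths are more frequent, and loses some power even if they are not.
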